measures of treatment effect will include treatment retention, Addiction Severity Index (ASI)-Lite score, Hamilton Depression Rating Scale (HAM-D) score, Brief Substance Craving Scale (BSCS) score, Methamphetamine Withdrawal Questionnaire (MAWQ), Clinical Global Impression scores as assessed by the subject (CGI-S) and an observer (CGI-O) and HIV risk taking behaviors using an HIV Risk-Taking Behavior Scale (HRBS). ASI-Lite is performed during screening and at study termination. The HAM-D is performed biweekly through screening, baseline, and treatment periods; it is also performed at study termination. The BSCS, CGI-S, and CGI-O are assessed weekly at screening, baseline and during treatment and also at study termination. The MAWQ is collected 3 times per week during baseline and the first two weeks of treatment and then weekly thereafter. The HRBS is assessed at screening and at study termination. There will also be neurocognitive battery done at screening and at study termination. Study agent compliance will be monitored by reconciliation of dispensed study agents. Treatment effects on other substances of abuse (amphetamines, cocaine, opiates, tetrahydrocannabinol, barbiturates, and benzodiazepines) will be determined by quantitative urinalysis at a central laboratory.

ANALYSIS: Each of the primary and secondary outcome variables will be analyzed using appropriate statistical methods for the intent-to-treat population and for the evaluable population. The intent-to-treat population includes subjects who are randomized and receive at least 1 dose of study agents. The evaluable population is those subjects who meet eligibility criteria and provide at least 6 urine specimens and 28 days of self-report of substance use (SUR). The individual effects, if any, of age, race, usual route of methamphetamine use (oral/nasal inhalation *versus* intravenous/smoked), and clinical site on the primary treatment effects will be determined where numbers permit. Interactions of these variables with gender, historical self-report of methamphetamine use (prior use in the last 30 days ≤ 18 *versus* > 18), and severity of depression (HAM-D score ≤ 12 *versus* >12) will also be assessed. Statistical tests will be two-sided at a 5% Type I error rate. Confidence intervals will be two-sided with a 95% confidence coefficient.

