was well tolerated and reduced self-reported craving for cocaine. A multicenter placebocontrolled double-blind clinical trial of bupropion for cocaine dependence in methadonemaintenance patients indicates efficacy of bupropion for the subgroup of patients with depression at study entry (Margolin *et al.*, 1995).

The results of animal studies designed to test the ability of bupropion to block effects of methamphetamine support clinical use for the treatment of methamphetamine dependence (Kim *et al.*, 2000). Thus, bupropion provides complete protection against methamphetamine-induced decrease in dopamine uptake in striatum in *in vitro* model of methamphetamine-induced dopamine nerve terminal toxicity. It is logical to postulate that combination of bupropion's dopaminergic activity and antidepressant properties may guarantee its efficacy in clinical trials for treatment and relief of the signs and symptoms of methamphetamine withdrawal and for prevention of the relapse.

Bupropion Pharmacokinetics. Tablets of bupropion hydrochloride come in immediate- and sustained-release (SR) formulations. The bupropion SR, 150 mg, twice daily formulation will be used for this study. Bupropion SR has been shown to be bioequivalent to 100 mg three times daily of the immediate release formulation with regards to rate and extent of absorption and parent drug and metabolites in clinical trials for depression. Better compliance is expected with twice daily dosing as opposed to thrice daily dosing making bupropion SR an obvious choice for study.

The half-life of bupropion is approximately 21 hours after chronic dosing. Peak plasma concentrations of bupropion are achieved within 3 hours following oral administration. It appears there is no clinically significant delay in absorption due to food. Steady state plasma concentrations of bupropion are reached within 8 days. Four basic metabolites have been identified. These metabolites are pharmacologically active, but their potency and toxicity relative to bupropion have not been totally characterized. They may be of clinical importance because the plasma concentration of metabolites is higher than those of bupropion.

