15.2 SECONDARY OBJECTIVES

Secondary objectives include:

- 1. Determining the safety of bupropion in the study population.
- 2. Assessing the efficacy of bupropion in other measures of success in the reduction of methamphetamine use including the proportion of successful subjects with 3 consecutive weeks of negative urine samples as measured by 9 consecutive negative urine samples for methamphetamine, the weekly mean proportion of non-use days assessed by self report of use, the largest number of consecutive methamphetamine non-use days, and reductions in use as compared to baseline.
- 3. Assessing the efficacy of bupropion in the reduction in the severity of methamphetamine dependence (assessed by ASI-Lite and self and observer scored CGI), craving (assessed by BSCS), severity of withdrawal symptoms (assessed by MAWQ), and severity of depression (assessed by HAM-D) as compared to placebo control.
- 4. Assessing the efficacy of the bupropion in reducing the proportion of use-days of other substances of abuse (opiates, marijuana, cigarette smoking, alcohol, and cocaine) as determined by SUR and the number of negative urines for other substances of abuse (amphetamines, cocaine, opiates, tetrahydocannabinol, benzodiazepines, and barbiturates) by urine drug screen or negative alcohol breathalyzer tests.
- 5. Assessing the effects on HIV risk taking behaviors.
- 6. Assessing the effects of bupropion on neurocognitive functions.
- 7. Assessing the reduction in methamphetamine use as a function of the resolution of depression in bupropion versus placebo groups.

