15.6 ANALYSIS PLAN

15.6.1 Efficacy Assessments

Each of the primary and secondary efficacy outcome measures will be analyzed for the intent-totreat and for the evaluable population. Major differences in the results, if any, will be further explored. While there is every intent to be complete in describing the analyses to be performed, it is not possible to anticipate every contingency and some adjustments may be required to meet constraints posed by the structure of the data.

Statistical tests will be two-sided at a 5% Type I error rate. Confidence intervals will be two-sided with a 95% confidence coefficient.

Primary Efficacy Outcomes

The weekly mean proportion of methamphetamine-free urines on study will be compared between treatment groups using Generalized Estimating Equations (GEE) for ordinal categorical response (Lipsitz *et al.*, 1994). GEE provide a model-based regression method applicable for the analysis of the correlated data that will result from this repeated measures longitudinal study. The GEE procedure was first proposed by Liang and Zeger (1986) and Zeger and Liang (1986) and models the population average. GEE has several useful features:

- 1. It can be used to analyze different types of outcomes such as continuous, binary, or count.
- 2. It can be used to analyze an unbalanced design caused by either differing numbers of observations per person or by observations taken at different times.
- 3. The parameter estimates are consistent even if assumptions about the variance structure are not completely accurate.

As a secondary analysis, the individual effects, if any, of age, race, site, and usual route of methamphetamine use (oral/nasal inhalation versus intravenous/smoked) on the primary treatment effects will be determined where numbers permit. The first order interactions of these variables with gender, historical self-report of methamphetamine use (prior use in the last 30 days ≤ 18 versus > 18), and severity of depression (HAM-D score ≤ 12 versus >12) will also be included in the model. Presentation will include the full model with all terms and a reduced model containing only significant terms.

Secondary Efficacy Outcomes

Unless the primary response analysis implies the need for a more elaborate model, between group comparisons of the secondary outcomes will be performed as follows:

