15.9 POST HOC ANALYSES

Data will be collected in this study for scientific use and not as primary or secondary outcome measures. These data are being collected to build a database that will help characterize the study population. Additional post hoc analysis may be performed to evaluate other confounding factors on outcomes such as depression or patterns of methamphetamine use at baseline and after treatment. In addition, a post hoc analysis is anticipated by *a priori* developing an algorithm for determining use and non-use days by combining self-reports of use with urine methamphetamine levels. Clinical laboratory studies are currently in progress to evaluate the pharmacokinetics of methamphetamine urine clearance. Based on the results of these studies, it is anticipated that rules for assessing new use similar to those developed by Preston (1997) for cocaine will be developed for methamphetamine. These rules will then be applied to the dataset generated by this study for analysis.

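### The secondary effect-modifier model names covariate-by-covariate interactions instead of treatment by balancing factor (baseline depression included), and adds a model pruned by significance

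*Protocol*

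**What the plan says.** Protocol section 15.6.1 describes, as a secondary analysis of the primary outcome, a model with two layers of terms.

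- First layer: "the individual effects, if any, of age, race, site, and usual route of methamphetamine use" on the primary treatment effects, as far as numbers allow. This amounts to treatment-by-covariate terms for four variables.
- Second layer: "The first order interactions of these variables with gender, historical self-report of methamphetamine use" (30-day use split at 18 days) and depression severity (HAM-D split at 12). The synopsis (section 3) has the same construction: "Interactions of these variables with gender, historical self-report of methamphetamine use".

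On presentation it says: "Presentation will include the full model with all terms and a reduced model containing only significant terms". The general rule in the same section is: "Statistical tests will be two-sided at a 5% Type I error rate". It attaches no multiplicity rule to these terms.

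Baseline depression appears elsewhere as follows.

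- Section 4 cites a multicentre cocaine trial in methadone-maintained patients that "indicates efficacy of bupropion for the subgroup of patients with depression at study entry".
- Section 8.4 makes the HAM-D stratum one of three balancing factors, with gender and prior use.
- Section 15.2, objective 7, reads: "Assessing the reduction in methamphetamine use as a function of the resolution of depression in bupropion versus placebo groups".
- Section 15.9 reads: "Additional post hoc analysis may be performed to evaluate other confounding factors on outcomes such as depression", and goes on to mention use patterns at baseline and after treatment.

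**The concern.** A term such as site by gender, or race by HAM-D stratum, says how methamphetamine use differs across kinds of participant. It does not say who benefits from bupropion; that needs treatment in the interaction. The second layer leaves treatment out.

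The three factors judged important enough to balance at randomisation are therefore not named as modifiers of the treatment effect. One of them, baseline depression, is the only clinical subgroup for which the background reports an effect.

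The reduced model raises a separate difficulty. Once terms are kept because they were significant in the same data, their nominal p-values and intervals no longer carry their stated error rates.

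Section 15.7 says the enlarged trial is meant to help decide whether to study bupropion further and how to design the next study. Whether to focus on depressed users is a natural question at that point. The protocol names no pre-specified estimate that bears on it.

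**Working it through.** The protocol gives no power, effect size or standard deviation for the main comparison or for any interaction, so there is no figure to reproduce.

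**1. Which terms are named.** In both places the phrase 'these variables' refers back to age, race, site and route.

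| Interaction | Named in 15.6.1? |
|---|---|
| treatment × age, race, site, route | yes, implied by the first sentence |
| age, race, site, route × gender, prior use, HAM-D stratum | yes, 4 × 3 = 12 terms |
| treatment × HAM-D stratum | no |
| treatment × prior use | no |
| treatment × gender | no |

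**2. Model size.** Site has 5 levels (4 df); age and route take 1 df each. The number of race categories is not given; I assume 2 to 5 (1 to 4 df).

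- Covariate df: 1 + (1 to 4) + 4 + 1 = 7 to 10.
- Covariate × stratum df: 3 × (7 to 10) = 21 to 30.
- Total, with c covariate df: intercept 1 + treatment 1 + strata 3 + c + c (treatment × covariate) + 3c = 5 + 5c = 40 to 55 parameters, for 150 subjects. The four-level ordinal outcome would need thresholds in place of the single intercept.

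**3. Chance findings.** With m independent tests at 5% and all effects null, P(at least one) = 1 − 0.95^m and the expected number is 0.05m.

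| Unit tested | m | P(at least one) | Expected |
|---|---|---|---|
| whole terms | 12 | 46% | 0.6 |
| single coefficients, 2 race categories | 21 | 66% | 1.05 |
| single coefficients, 5 race categories | 30 | 79% | 1.5 |

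Independence is an approximation. A least-squares simulation of the all-null case checked it (150 subjects, one summary outcome each, 2 race categories, 40 parameters, assumed covariate prevalences, 4,000 replicates). At least one covariate-by-stratum coefficient was significant in 62% of trials, 1.04 on average, close to the 66% and 1.05 for m = 21.

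**4. Whether another section supplies the missing term.** Objective 7 relates drug use to the resolution of depression. That is a change after randomisation, not a baseline characteristic. Section 15.9 is optional, is labelled post hoc, and treats depression as a confounder. Neither pre-specifies treatment by baseline HAM-D stratum.

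**5. What adding the term would give.** It costs 1 df, and the stratum is needed for randomisation, so it will be known for every subject. Take 1:1 allocation, outcome SD 1, N = 150 and an assumed share q with HAM-D above 12.

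- SE(main) = 2/√150 = 0.163.
- SE(interaction) = √(4/(Nq) + 4/(N(1 − q))).
- q = 0.5: √(4/75 + 4/75) = 0.327, which is 2.0 times the main-effect SE.
- q = 0.2: √(4/30 + 4/120) = 0.408, which is 2.5 times.
- Detectable with 80% power at two-sided 5%: 0.91 SD (q = 0.5) to 1.14 SD (q = 0.2), against 0.46 SD for the main effect.
- Power for a 0.5 SD interaction: 33% (q = 0.5) to 23% (q = 0.2).

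**The case against.** The strongest reply is that a separate SAP may add treatment by HAM-D stratum, and that section 15.6.1 does not claim a complete list. This does not dispose of the point. The protocol itself names the interaction terms and the selection rule, and section 16.3 ties the analysis to the protocol's analytical plan. The fault lies in what is fixed, not in a detail left for later.

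A second reply is that the paragraph is about effects on the treatment effect, so the second sentence may intend three-way terms (treatment by covariate by stratum). The wording speaks of first-order interactions, which points the other way. Even on the three-way reading, treatment by HAM-D stratum is not named, and the model would be larger still.

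Several limits do stand, and they rule out stronger readings that a reader might infer.

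- That the plan examines no treatment-effect modification at all: the first sentence covers four covariates.
- That only a data-selected model will be published: the full model is presented too, and nothing says conclusions will rest on the reduced one.
- That the primary result is compromised: this is a secondary analysis, restricted to what the numbers allow.
- That depression is left wholly to post hoc work: HAM-D is a balancing factor, a secondary outcome, the subject of objective 7 in its change over time, and present in the secondary model. Only the treatment-by-baseline term is missing.
- That the background establishes a subgroup effect here: it cites one cocaine trial in methadone-maintained patients, and section 4 itself says carry-over of cocaine treatments to methamphetamine users is largely unknown. That is a reason to pre-specify the term, not evidence of an effect.

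**Conclusion.** The point holds in a limited form. As worded, the second sentence fixes 12 covariate-by-covariate interactions that cannot show who responds to bupropion, while the three treatment-by-balancing-factor interactions go unnamed. The reduced model reports inference that ignores selection.

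The chance of at least one spurious covariate-by-stratum interaction is about 46% if whole terms are tested, and about 66% to 79% if single coefficients are. Both figures assume that all effects are null and the tests independent; the second also assumes 2 to 5 race categories. The upper range should not be quoted alone, because the protocol speaks of terms without saying how a multi-level term is judged.

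It would also be too strong to say that the missing term would have settled whether depressed users benefit. With an interaction SE 2.0 to 2.5 times that of the main effect, it would give an estimate with a wide interval, not a powered test. The change is worth making because it costs almost nothing, not because the primary conclusion is at risk.

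**What to change.** In section 15.6.1, and in the matching sentence of the synopsis:

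1. Replace the covariate-by-stratum sentence with three named interactions: treatment by HAM-D stratum (listed first), treatment by prior use, and treatment by gender. Add each one separately to the primary GEE model, together with its main effect.
2. Keep the treatment by age, race, site and route terms already implied by the first sentence, and say explicitly that they are interactions with treatment.
3. Report each interaction, and the treatment effect within each level, with 95% confidence intervals. Label them all exploratory.
4. Delete the reduced model that keeps only significant terms.

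The cost is a short wording change, with no new data and less modelling. Two drawbacks remain. The interaction estimates will be imprecise, as shown above. Seven separate interactions at 5% would still carry about a 30% chance of at least one false positive if independent and all null (1 − 0.95^7 = 0.30), which is why they should be read as estimates and not as tests.

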13.3 ASSESSMENTS DURING TREATMENT

Over the 12-week period of treatment, subjects will return to the clinic three times per week (ideally on Monday, Wednesday, and Friday). Assessments will be performed as follows:

At each visit:

- 1. SUR
- 2. Urine methamphetamine and creatinine
- 3. Alcohol breathalyzer
- 4. AEs
- 5. MAWQ (the first two weeks only)

- 6. Concomitant medications
- 7. Treatment compliance (study agents and CBT)

Once per week preferably at the first visit of each week:

- 1. Urine toxicology screen using an onsite testing device
- 2. Urine toxicology screen (urine specimen sent to NWT for analysis)
- 3. BSCS
- 4. CGI-S
- 5. CGI-O
- 6. MAWQ (starting at week 3 for the first two weeks it is collected 3 times per week)
- 7. Vital signs

At weeks 4 and 8, preferably at the first visit of the week:

1. Pregnancy test

At week 2, 4, 6, 8, 10 and 12, preferably at the first visit of the week:

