Following randomization, during the treatment phase of the study and at each of the follow-up visits, urine will be collected 3 times per week (generally Monday, Wednesday, and Friday, barring holidays and schedule conflicts) and NWT will screen the first sample collected each week for cocaine, methamphetamine/amphetamines, tetrahydrocannabinol, barbiturates, opiates, and benzodiazepines. NWT will screen all samples for amphetamines/methamphetamine and quantitative creatinine, and NWT will quantitate amphetamines and methamphetamine for all samples, which screen positive by NWT for methamphetamine/amphetamines.

All specimens collected during this time frame and screened positive by NWT for methamphetamine/amphetamines will be subjected to methamphetamine quantitative analysis performed at NWT for the determination of "new use." The back-up sample retained at the site will be stored frozen until the NIDA data-coordinating center has notified the site that it can be disposed.

Urine Toxicology Screen Using an Onsite Testing Device. During the screening and baseline period, urine will be collected 3 times per week (generally Monday, Wednesday, and Friday, barring holidays and schedule conflicts). After the backup aliquot and central laboratory testing aliquot has been taken, these samples will be analyzed using an on-site testing device (tetrahydrocannabinol, methamphetamine, cocaine, amphetamines, barbiturates, opiates, benzodiazepines, tricyclics, and phencyclidine). Samples positive for amphetamine (the onsite testing device has a cutoff of greater than or equal to 1000 ng/mL) will be considered as positive for methamphetamine for inclusion criteria purposes.

During treatment and after the backup aliquot and central laboratory testing aliquot has been taken, the first urine sample collected each week will be analyzed using an on-site testing device.

A frozen aliquot of every sample will be stored at the site. At treatment termination and followup, samples will be sent to a central lab for analysis, be subjected to onsite testing, and an aliquot will be frozen on site as back up. Results of on-site testing will be provided to the clinical staff as well as the investigative staff for the safety of the subjects.

Medical Urinalysis. Urine will be collected and analyzed for specific gravity, pH, blood, protein, glucose, ketones, leukocytes, and nitrites. The analysis will be conducted at a central clinical laboratory.

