15.4.2 Secondary Outcomes Measures

Effect on methamphetamine and other drug use during the 12-week treatment period

- **A.** Log weekly median quantitative methamphetamine level.
- **B.** The proportion of successful subjects with different patterns in the reduction in drug use examined as follows:
 - 1. Proportion of subjects with 3 consecutive weeks of abstinence as measured by 9 consecutive methamphetamine negative urine samples.
 - 2. Proportion of subjects who reduce the overall proportion of methamphetamine quantitative urine concentration to 50% or less of his/her baseline rate.
 - 3. Proportion of subjects who reduce the overall proportion of methamphetamine quantitative urine concentration to 25% or less of his/her baseline rate.
- **C.** Weekly mean proportion of methamphetamine non-use days based on subjects self report of use (SUR) during the 12-week treatment period.

- **D.** The maximum number of consecutive methamphetamine non-use days by subjects self report of use (SUR).
- **E.** The proportion of methamphetamine negative urines during the 12-week period.
- **F.** Weekly mean proportion of non-use days of other drug use, by other drug according to SUR.
- G. Proportion of negative urines or alcohol breathalyzer results for other drug use, by drug.

Reduction in the severity of methamphetamine dependence, craving, and withdrawal

- H. CGI-O scores.
- I. CGI-S scores.
- J. ASI-Lite scores.
- K. BSCS scores.
- L. MAWQ scores

Severity of Depression

M. HAM-D scores.

Changes in Cognitive Functions

N. Change in cognitive function at study end compared to baseline.

HIV Risk Taking Behaviors

O. Change in HRBS scores since baseline.

Treatment Retention

P. Number of days in treatment.

Safety of Bupropion

Q. AEs, laboratory data, physical exams, and vital signs.

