- 1. Log weekly median quantitative methamphetamine, weekly mean proportion of methamphetamine non-use days by self-report, weekly mean proportion of non-use day of other drug use, measures A, C, and F, will be assessed by GEE.
- 2. Proportion of successful subjects and negative urines for other drugs or alcohol breathalyzer tests, measures B and G, will be assessed by Chi-square tests.
- 3. The maximum number of consecutive methamphetamine non-use days, proportion of methamphetamine negative urines, change in cognitive function, and change in HRBS scores at termination compared to baseline measures D, E, N, and O will be assessed by t-test.
- 4. Repeated measures of CGI-S, CGI-O, BSCS, ASI-Lite, MAWQ, and HAM-D scores, measures H, I, J, K, L, and M will be assessed by GEE.
- 5. Survival analysis will be performed on retention data (measure P). The Wilcoxon (Gehan) test will be used to test the hypothesis that the survival distribution of the bupropion group will be the same as those of the placebo group.
- 6. Adverse events, laboratory data, physical exams, and vital signs will be reported in tabular form. AEs will be listed indicating the frequency of each type of event by various demographic characteristics such as gender, ethnicity, age, duration of addiction, other medical problems both related to and independent of the addiction, and combinations of these characteristics. The frequencies of adverse events by type will be compared between study arms using Chi-square analyses.

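### Measure G (other-drug urines and breathalyzer results) is assigned a chi-square test, which does not hold the stated 5% level when up to about 12 or 36 correlated results per subject are pooled

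*Protocol*

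**What the plan says.** Section 15.4.2 of the protocol defines measure G as "Proportion of negative urines or alcohol breathalyzer results for other drug use, by drug". This corresponds to secondary objective 4 in section 15.2, which counts "negative urines for other substances of abuse (amphetamines, cocaine, opiates, tetrahydocannabinol, benzodiazepines, and barbiturates) by urine drug screen", or negative breath tests.

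Section 15.6.1, item 2, fixes the test: "Proportion of successful subjects and negative urines for other drugs or alcohol breathalyzer tests, measures B and G, will be assessed by Chi-square tests". Measure B, in the same sentence, classifies each subject once as a success or not. No such classification of subjects is defined for G.

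The testing schedule gives many results per subject. On the urine side, section 13.6.14 says "NWT will screen the first sample collected each week for cocaine, methamphetamine/amphetamines, tetrahydrocannabinol, barbiturates, opiates, and benzodiazepines". For breath tests, section 13.3 says "Over the 12-week period of treatment, subjects will return to the clinic three times per week" and lists the breathalyzer among the assessments done at every visit.

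The level is set in section 15.6.1: "Statistical tests will be two-sided at a 5% Type I error rate".

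The same section handles G's closest neighbours differently. Measure F, self-reported non-use days for other drugs, goes to GEE. Measure E, the proportion of methamphetamine-negative urines, goes to a t-test. The section also justifies GEE by the correlation that repeated observations on a subject will show.

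**The concern.** A chi-square test comparing negative with positive results between arms needs independent results. Repeated tests on one person are not independent. A regular cannabis user tends to test positive week after week, and section 9.2 allows marijuana dependence at entry. The pooled test takes its standard error from the number of specimens, which overstates the information in the data, so it rejects too often when the drug has no effect.

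At stake is the urine and breath component of secondary objective 4. It is tested drug by drug, so each drug and alcohol carries its own excess chance of a spurious treatment difference.

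**Working it through.** **Inputs from the protocol**
- Nominal level: 5%, two-sided (15.6.1).
- Drug screens per subject: 1 per week × 12 weeks = 12 (13.6.14).
- Breath tests per subject: 3 per week × 12 weeks = 36 (13.3).
- Termination assessments (13.4) would add one of each; they are left out here.
- Sample size: 150 in two arms (section 3), taken as 75 per arm.
- Dropout: 46% to 50% (15.7), taken as 48%.

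**Assumed input.** The ICC of results within a subject is not given. It is varied from 0.01 to 0.5.

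**Formulas.** Design effect DE = 1 + (m − 1) × ICC. True error rate = 2 × [1 − Φ(1.96 / √DE)].

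The protocol derives no figure for G to reproduce. With ICC = 0, DE = 1 and the formula returns 5.0%, so the nominal level is right only if results are independent.

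Example for urines at ICC 0.3: DE = 1 + 11 × 0.3 = 4.3; 1.96 / √4.3 = 0.945; error rate 34.5%. Example for breath tests at ICC 0.1: DE = 1 + 35 × 0.1 = 4.5; 1.96 / √4.5 = 0.924; error rate 35.6%.

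| ICC (assumed) | DE, m = 12 | True rate, urines | DE, m = 36 | True rate, breath tests |
|---|---|---|---|---|
| 0.01 | 1.11 | 6.3% | 1.35 | 9.2% |
| 0.05 | 1.55 | 11.5% | 2.75 | 23.7% |
| 0.1 | 2.1 | 17.6% | 4.5 | 35.6% |
| 0.3 | 4.3 | 34.5% | 11.5 | 56.3% |
| 0.5 | 6.5 | 44.2% | 18.5 | 64.9% |

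**ICC at which the rate triples to 15%.** This needs DE = (1.960 / 1.440)² ≈ 1.85. Then ICC = 0.85 / 11 ≈ 0.078 for urines and 0.85 / 35 ≈ 0.024 for breath tests.

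**Simulation check.** Beta-binomial data were generated with no treatment effect: 75 per arm, assumed negative rates of 70% and 90%, 20,000 trials per setting.
- With complete data, the pooled test agreed with the table to within 1 percentage point.
- With 48% dropout at a uniformly distributed time, the mean number of results fell to about 9.4 (urines) and 27.6 (breath tests). The pooled test still rejected in about 16% and 34% of trials at ICC 0.1, and in about 32% and 54% at ICC 0.3.
- A t-test on per-subject proportions rejected in 4.6% to 5.3% of trials, and a robust test clustered on subject in 4.9% to 5.7%, across all settings including dropout.

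**The case against.** The strongest reply is that section 15.6.1 names a test and not a unit of analysis. A chi-square test in each week separately, or one comparing subjects whose results were all negative, would use one result per subject and be valid. A SAP, not available here, might specify one of these. It is true that the protocol never says in words that specimens are pooled. But neither alternative is in the text. G is defined as a proportion of results, objective 4 counts negative urines, and section 16.3 says the analysis follows the protocol's analytical section. Applied as written, the definition and the test together lead to pooling.

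Section 15.6.1 also allows a fuller model if the primary response analysis calls for one, and unspecified adjustments to suit the data. Neither clause addresses clustering in G, and the first depends on a different outcome.

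The size can be challenged too. The ICC is assumed, would differ by drug, and at 0.01 the inflation is only 1.3-fold (urines) to 1.8-fold (breath tests). This stands, and the result has to be given as a range.

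Finally, G is one of 17 secondary measures (A to Q), and section 15.3 describes the objectives as exploratory. This limits the consequence but does not make the test valid.

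**Conclusion.** The test fixed for measure G is wrong as written. With results pooled, the true two-sided error rate runs from about 6% to 44% for urines and from about 9% to 65% for breath tests as the assumed ICC goes from 0.01 to 0.5. It is at least three-fold above an ICC of about 0.08 or 0.025. The figures assume equal arms and a common correlation between any two results of a subject. The simulation also assumes that dropout is unrelated to use, and it did not cover drugs with positive rates below 10%.

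Four stronger readings are not supported:
- **That inflation by several-fold is established.** It depends on an ICC the protocol does not give.
- **That objective 4 cannot be answered.** Its self-report component is measure F, which is analysed by GEE. The primary test is not touched either.
- **That the adverse-event comparison has the same fault.** Section 15.6.1 says "The frequencies of adverse events by type will be compared between study arms using Chi-square analyses", without stating whether events or subjects are counted, so no error is shown.
- **That listing amphetamines among other drugs duplicates the primary outcome.** The rule in section 13.6.14 says an amphetamine-positive onsite sample "will be considered as positive for methamphetamine for inclusion criteria purposes". That is an eligibility rule and does not define an outcome.

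**What to change.** In section 15.6.1, item 2, keep chi-square for measure B and move measure G elsewhere. Either of two methods already in the protocol will do:
- binary GEE with robust standard errors clustered on subject, as an extension of the GEE planned for F; or
- each subject's proportion of negative results, compared between arms by t-test, as for E.

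Choose one in advance. Under dropout they can weight subjects differently: the t-test counts each subject once, whereas GEE can give more weight to subjects with more results. No covariates are needed for this repair; section 15.6.1 brings them in only for a secondary analysis of the primary outcome.

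The cost is one sentence, settled before unblinding. No data collection changes.
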